10.2. Study Intervention Compliance

Define how adherence to the protocol (e.g., administration of study intervention, use of device,) will be assessed, and verified (if applicable, e.g., plasma assays, electronic monitoring devices, daily diaries).

Participants will be monitored continuously throughout the 3 hours study intervention timeline by either a licensed dentist or licensed registered nurse. Administration of the Epidiolex study drug or Placebo will be achieved by a licensed dentist. All study personnel will be fully calibrated as to the study requirements/standards prior to initiation of the study. Each participant will be assigned a pre-numbered study packet containing all study required case report forms, including the questionnaires with assigned administration times clearly noted at the top of the document. A study 'Time Out' will occur to review that all study documentation has been completed and the appropriate randomization has occurred prior to escorting the participant to the operatory for the dental procedure.

10.3. Permitted Concomitant Therapy

This section should be consistent with the medication restrictions in the inclusion/exclusion criteria previously listed. Describe how allowed concomitant therapy might affect the outcome (e.g., drug-drug interaction, direct effects on the study endpoints).

Ibuprofen 600mg and acetaminophen/codeine 650/60mg if a contraindication for 600mg ibuprofen exists, will be allowed in the trial.

These medications will be given at patient's request as a rescue medication during the observation period. We do not expect any drug-to drug interaction with these medications.

These analgesics will reduce the pain levels. To that end we will perform a time-to-rescue analysis. The subjects will complete the study.

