
1. Primary outcome measure: a.VAS pain intensity differences from baseline among the groups at each time point and maximum pain relief.
 
b.Bite Force measurement using the Bite Fork at baseline, 1.5 h, 3h and 7d.
 
2. Secondary outcome measure: Measure psychoactive effects, mood changes at 0, 1.5h and 3h points, and somnolence at 3h and 1- week time point.
	
1. Patients will report their pain level using a 100mm Visual Analogue Scale (VAS) at 0, 15min, 30min, 45min, 1h, 1.5h, 2 and 3 hour and 1week post-administration visit time of study drug Epidiolex or Placebo.
 
2. Patients will report their pain level that is elicited by biting down on the Bite Fork at 0, 1.5h, 3h and 1week post-administration visit time of study drug Epidiolex or Placebo.
 
2. Patients will report feelings of drug high, alterations in internal perception and alterations in external perception, along with alertness, contentment and calmness by completing the following questionnaires:
 
a. Bowdle questionnaire b. Bond & Lader Mood Scale c. Epworth Sleepiness Scale
	
1. The VAS has been shown to be sensitive to changes in a patient's pain experience, is easily understood and easy to use. It has been successfully used in various health fields in children and adults.
 
2. The bite force measurement provided additional pain information being able to isolate one particular tooth (the problem tooth) being studies.
 
2. The three listed questionnaires are commonly used for psychedelic assessment and safety assessment of cannabinoids use, with a longstanding administration in previous published studies in medical journals such as "Pain", "CNS Drugs", and "Journal of Psychopharmacology". Such effects are not commonly associated with CBD use because of the inherent nature of the absence of THC based on current literature. Nevertheless, patients that report such adverse events at the end of the observation period will be asked to have a family member to accompany them home.

4. Rationale Briefly state the reason for conducting the clinical trial.			

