2. Self-reported prior experience inhaling cannabis (either via smoking or vaporization). Cannabis trials often present with high placebo effect. Cannabis naïve subjects are thus proposed to minimize this effect as well the possibility of tachyphylaxis.

3. Use of opioids in the month prior to screening/treatment visit, and/or NSAIDS or acetaminophen 6 hours prior to treatment. Any analgesic can potentially mask the effects of the study drug and increase placebo effect.

Continued Study Monitoring and Halting Rules:

Study drug is administered one time only at study hour zero with monitoring for the next three hours. Once the assigned study drug is given, the subject will continue in the 3-hour study observation period, even if they request the rescue medication. Only if they specifically request to formally withdraw from the study will they proceed to the dental treatment early, however subjects will be asked to complete the 3rd hour pain and Psychoactive Assessment Questionnaires at the time of consuming the rescue medication. Each patient is different in regards to their pain endurance level, so subjects will be instructed to request rescue medication when their pain becomes uncomfortable. Subjects will be encouraged to wait at least 60 minutes after the one time administration of the study drug before consuming any rescue medication. Subjects will additionally be asked to attend the one-week follow-up visit and complete the VAS and Sleepiness Scale Assessment.

In the case that a serious event appears within the same arm more than three times, we will discontinue the arm of the study. The PI will unblind the cases for close monitoring of the adverse event.

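### Pain scores after rescue analgesia have no stated handling rule, and Section 11.1 can file a score taken at rescue as the 3 h score

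*Combined protocol and SAP*

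**What the plan says.** Section 3 of the combined protocol and SAP makes the primary outcome "VAS pain intensity differences from baseline among the groups at each time point and maximum pain relief". VAS is taken at 0, 15, 30 and 45 min, at 1, 1.5, 2 and 3 h, and at 1 week. Bite-elicited pain is reported when "biting down on the Bite Fork at 0, 1.5h, 3h and 1week post-administration visit time".

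On rescue, Section 10.3 states: "These analgesics will reduce the pain levels. To that end we will perform a time-to-rescue analysis. The subjects will complete the study". Section 11.1 says that "the subject will continue in the 3-hour study observation period, even if they request the rescue medication". It adds only a soft delay: "Subjects will be encouraged to wait at least 60 minutes after the one time administration of the study drug".

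Section 11.1 then says: "Only if they specifically request to formally withdraw from the study will they proceed to the dental treatment early, however subjects will be asked". The sentence continues: "subjects will be asked to complete the 3rd hour pain and Psychoactive Assessment Questionnaires at the time of consuming the rescue medication". Section 10.2 describes study packets "including the questionnaires with assigned administration times clearly noted at the top of the document".

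Section 12.3 includes all participants, plans sensitivity analyses only for age and sex imbalance, and uses generalized estimating equations to find the time of maximum analgesia. Section 12.4 specifies mixed models for primary and secondary outcomes, and Kaplan-Meier curves with stratified log-rank tests for time to rescue. Neither section says how a score recorded after rescue is to be treated.

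**The concern.** There are two linked gaps.

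The first is analytic. Continued observation, inclusion of everyone and the absence of any exclusion rule together imply that post-rescue scores are analysed as observed, though the plan never says so. The later CBD-placebo contrasts then mix the effect of CBD with that of ibuprofen or acetaminophen/codeine, and no planned analysis shows how much of the difference depends on rescue.

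The second is about data collection. The third-hour form is tied to the moment of rescue. The clause follows the sentence on formal withdrawal, so it may cover only patients who withdraw or every rescued patient. Either way, a score from about 1-2 h can sit on a form labelled 3 h. On the wider reading, a rescued patient who stays to 3 h may have no true 3 h score, and that cannot be recovered later.

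This matters because the pilot is meant to supply the effect size (12.2), the sample-size inputs and endpoint choice (12.4) and the time of maximum analgesia (12.3) for a definitive trial.

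**Working it through.** **The plan's own figure.** There is none to reproduce. The 22 per group in Section 12.2 is a convenience sample with no effect size, SD or rescue rate. Every input below except 22 per group and the visit times is an assumption.

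**Simple formula.** As observed, shift = (placebo rescue rate − CBD rescue rate) × VAS drop from rescue.
- A gap of 10 points and a 15 mm drop: 0.10 × 15 = 1.5 mm.
- A gap of 30 points and a 25 mm drop: 0.30 × 25 = 7.5 mm.
- A gap of 18 points: 0.18 × 15 = 2.7 mm, and 0.18 × 25 = 4.5 mm.
- Equal rates: no shift.

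**Simulation inputs.** 440,000 patients per arm, with baseline-adjusted differences.
- Baseline is N(65, 18) limited to 30-100 mm.
- The placebo drop is 10 mm and the extra CBD drop 15 mm (13.7 mm after limiting VAS to 0-100). Both rise linearly to 1.5 h and are flat afterwards.
- Between-patient SD is 20 mm and within-patient SD 12 mm.
- Rescue is requested at 1, 1.5 or 2 h when VAS reaches a threshold. It lowers VAS by 15 or 25 mm, building over 1 h.
- The threshold is 55 or 65 in both arms, or differs by arm (placebo 62, CBD 48; placebo 70, CBD 42).

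**CBD-placebo differences (mm).** Carried means that post-rescue scores are replaced by the pre-rescue score.

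| Rescue, placebo vs CBD | 3 h true | 3 h as observed | 3 h carried | Max relief true | Max relief as observed | Max relief carried |
|---|---|---|---|---|---|---|
| 66% vs 48%, or 52% vs 34% | 13.7 | 9.2-11.0 | 12.4-13.4 | 11.4 | 8.8-10.4 | 9.7-10.5 |
| 56% vs 58% | 13.7 | 13.9 | 11.3 | 11.4 | 12.5-12.6 | 7.8 |
| 45% vs 66% | 13.7 | 16.7-18.5 | 10.2 | 11.4 | 14.5-16.0 | 6.1 |

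In the first row the as-observed difference is 11.9-12.7 mm at 1.5 h and 9.9-11.5 mm at 2 h. The 1 h difference does not move, but only because no simulated patient takes rescue earlier. The 3 h shrinkage is 13.7 − 11.0 = 2.7 mm to 13.7 − 9.2 = 4.5 mm, matching the simple formula. Repeat runs moved the 3 h figures by no more than about 0.5 mm, hence roughly 2-5 mm. No bite effect was quantified.

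**If every rescued patient fills in the third-hour form at rescue.** The 3 h difference is 12.4-13.4 mm, the same as the carried result, so the contrast hardly shrinks. The level is wrong for 3 h, though: means are 59-60 mm (placebo) and 46-47 mm (CBD), against true 3 h means of 54.6 and 40.9 mm.

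**Against sampling error.** With SD 25 mm, SE = 25 × √(2/22) = 7.5 mm. With the model's as-observed SD of 17.5-18.5 mm it is 5.3-5.6 mm. The 2-5 mm shift is below both.

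**Planning consequence.** n per arm = 2 × (SD × 2.8016 / d)², for 80% power at two-sided 5%. Rescue lowers the highest scores, so the SD falls as well as the difference.
- No rescue: SD 21.5, d 13.7: 2 × (21.5 × 2.8016 / 13.7)² = 38.7, so 39.
- As observed, 15 mm drop: SD 18.5, d 11.0: 44.4.
- As observed, 25 mm drop: SD 17.5, d 9.2: 56.8.
- Unrounded simulation output gives about 44-56 as observed, and 48-53 for the carried analysis (SD 22.8-23.5).

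**The case against.** The strongest reply is that the plan already recognises rescue. It says that pain will fall, keeps collecting data and compares time to rescue between arms, so an imbalance would be visible. Analysing scores regardless of rescue is a legitimate choice. If the definitive trial also allows rescue and analyses scores that way, the as-observed difference is the right planning input. All of this stands. What is missing is the statement of that choice and one analysis showing how much it matters.

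It is also fair that carrying the pre-rescue score is not always closer to the no-rescue truth. With near-equal rescue, as-observed is off by 0.2 mm at 3 h and carried by 2.4 mm. That is why carried should be a sensitivity analysis only.

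A reader might infer that as-observed planning would roughly double the later trial. Holding the SD at 25 mm gives 53 per arm from 13.7 mm against 82-116 from 11.0-9.2 mm. That does not hold. Letting the SD fall with rescue gives about 39 against 44-56, and the gap counts as an error only if the no-rescue contrast is the target, which Sections 12.2 to 12.4 do not say.

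A reader might also infer that rescue will move the time of maximum analgesia. It may, but the simulated drift to 3 h depends on assuming flat pain after 1.5 h and on reading maximum analgesia as the lowest within-arm mean, which Section 12.3 does not define.

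**Conclusion.** The point holds in a limited form. Followed as written, the plan yields later VAS, bite and maximum-relief results that can include rescue, and for some or all rescued patients a third-hour score taken at another time. The time-to-rescue analysis does not change either.

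Under the assumed inputs the 3 h difference shrinks by roughly 2-5 mm when placebo patients take more rescue, is almost unchanged with equal use, and rises by 3.0-4.8 mm (16.7 − 13.7 to 18.5 − 13.7) when CBD patients take more. Larger assumptions give more: with a 20 mm effect, rescue in 65% vs 30% and a 30 mm rescue drop, the 3 h difference falls from 18.8 to 9.0 mm. The documents supply none of these inputs.

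They do not support saying that the plan is biased against CBD, that as-observed analysis is wrong, or that every rescued patient's 3 h score will be lost. The direction depends on who takes rescue, and the scope of the Section 11.1 clause is unclear. Severity is minor to should-fix. The collection rule is the more pressing part, because it cannot be repaired after the visit.

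**What to change.** **Section 11.1.** Record the clock time of rescue and a VAS immediately before it, on a separate at-rescue form. Still take the true 3 h assessment in everyone under observation. For patients who withdraw, record the at-rescue or exit score with its actual time and do not file it as 3 h.

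**Section 12.4.** State that the main analysis of the 0-3 h VAS and maximum relief uses scores as observed, regardless of rescue. Add one sensitivity analysis in which post-rescue scores are replaced by the pre-rescue score. Show the Section 12.3 timepoint result both ways.

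**Cost.** Wording, one extra VAS mark per rescued patient and one extra analysis. No extra patients are needed, and rescue times are already required for the Kaplan-Meier curves. The drawback is that the carried analysis is itself biased. In the simulation it was about 0-1 mm too low at 3 h with a common rescue threshold and 2-3.5 mm too low when thresholds differed by arm. For maximum relief it was 0.9-1.7 mm and 3.6-5.3 mm too low.

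**Separate documentation point.** Section 7 gives acetaminophen 500 mg as the alternative rescue drug, while 8.1, 10.3 and 10.4 give acetaminophen/codeine 650/60 mg when ibuprofen is contraindicated. Align Section 7 with the others, keeping an alternative for patients who cannot take ibuprofen.

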10.4. Rescue Medicine

List all medications, treatments, and/or procedures that may be provided during the study for "rescue therapy" and relevant instructions.

N/A, no rescue medicine

Ibuprofen 600mg (or acetaminophen/codeine 650/60mg, if 600mg contraindication for ibuprofen exists) will be provided in the 3-hour observation period as a rescue medication, if needed.

11. Study Intervention Discontinuation

11.1. Discontinuation of Study Intervention

Describe the criteria for discontinuing the study intervention (e.g., halting rules), including any monitoring test(s) and associated clinical decision point(s). Include reasons for temporary discontinuation of the study intervention (e.g., type and quantity of adverse events), clearly stating the length of time, if applicable, and describe the data to be collected at the time of study intervention discontinuation and approaches for restarting administration of or re-challenging with study intervention.

Participant safety monitoring, source documentation review and decision to discontinue study intervention will be under the oversight of the PI. Subjects will be monitored at each study visit/study follow up for any potential AE's or SAE's. To further

minimize risk to subjects and subsequent study discontinuation, the following medications will be screened for and restricted during the study intervention:

Patients on drugs metabolized by enzymes that also metabolize CBD (e.g. clobazam, diazepam, topiramate, warfarin). Epidiolex is metabolized by CYP3A4 and CYP2C19 and has the potential to inhibit CYP2C8, CYP2C9, and CYP2C19 at clinically relevant concentrations, therefore we chose to avoid potential drug interactions.

Info copied from drug prescription: **Effect of Other Drugs on EPIDIOLEX**

Moderate or Strong Inhibitors of CYP3A4 or CYP2C19

EPIDIOLEX is metabolized by CYP3A4 and CYP2C19. Therefore, coadministration with a moderate or strong inhibitor of CYP3A4 or CYP2C19 will increase cannabidiol plasma concentrations, which may result in a greater risk of adverse reactions.

Strong CYP3A4 or CYP2C19 Inducers

Coadministration with a strong CYP3A4 or CYP2C19 inducer will decrease cannabidiol plasma concentrations, which may lower the efficacy of EPIDIOLEX.

Effect of EPIDIOLEX on Other Drugs

UGT1A9, UGT2B7, CYP1A2, CYP2B6, CYP2C8, CYP2C9 and CYP2C19 Substrates

1. In vitro data predict drug-drug interactions with CYP1A2 substrates (e.g., theophylline, caffeine), CYP2B6 substrates (e.g., bupropion, efavirenz), uridine 5' diphospho-glucuronosyltransferase 1A9 (UGT1A9) (e.g., diflunisal, propofol, fenofibrate), and UGT2B7 (e.g., gemfibrozil, lamotrigine, morphine, lorazepam) when coadministered with EPIDIOLEX. Coadministration of EPIDIOLEX is also predicted to cause clinically significant interactions with CYP2C8 and CYP2C9 (e.g., phenytoin) substrates.

2. Self-reported prior experience inhaling cannabis (either via smoking or vaporization). Cannabis trials often present with high placebo effect. Cannabis naïve subjects are thus proposed to minimize this effect as well the possibility of tachyphylaxis.

3. Use of opioids in the month prior to screening/treatment visit, and/or NSAIDS or acetaminophen 6 hours prior to treatment. Any analgesic can potentially mask the effects of the study drug and increase placebo effect.

Continued Study Monitoring and Halting Rules:

Study drug is administered one time only at study hour zero with monitoring for the next three hours. Once the assigned study drug is given, the subject will continue in the 3-hour study observation period, even if they request the rescue medication. Only if they specifically request to formally withdraw from the study will they proceed to the dental treatment early, however subjects will be asked to complete the 3rd hour pain and Psychoactive Assessment Questionnaires at the time of consuming the rescue medication. Each patient is different in regards to their pain endurance level, so subjects will be instructed to request rescue medication when their pain becomes uncomfortable. Subjects will be encouraged to wait at least 60 minutes after the one time administration of the study drug before consuming any rescue medication. Subjects will additionally be asked to attend the one-week follow-up visit and complete the VAS and Sleepiness Scale Assessment.

In the case that a serious event appears within the same arm more than three times, we will discontinue the arm of the study. The PI will unblind the cases for close monitoring of the adverse event.

11.2. Continued Follow-up Discontinuation of Study Intervention

Describe efforts that will be made to continue follow-up of participants who discontinue the study intervention, but remain in the study for follow-up, especially for safety and efficacy study endpoints (if applicable). Reasonable efforts must be made to undertake protocol-specified safety follow-up procedures to capture adverse events (AE), serious adverse events (SAE), and unanticipated problems involving risks to subjects or others (UPIRSOs).

We will have a follow-up study visit 1 week after intervention to assess safety and ask them to complete a survey in redcap to report adverse events or unanticipated problems. The PI will proceed with unblinding of the subject's group depending on the nature and severity of the adverse event. The patient will be instructed to contact their physician or visit the urgent care clinic to address any medical event.

12. Statistical Considerations

12.1. Statistical Hypotheses

State the formal and testable null and alternative hypotheses for primary and key secondary endpoints, specifying the type of comparison (e.g., superiority, equivalence or non-inferiority, dose response) and time period for which each endpoint will be analyzed.

We hypothesize that Epidiolex will provide substantial pain relief for the patients presenting with emergency odontalgia in our clinical research facility.

12.2. Sample Size Determination

Include number of participants to recruit, screen, and enroll to have adequate power to test the key hypotheses for the study. Provide all information needed to validate your calculations and judge the feasibility of enrolling and following the necessary number of participants.

This is a pilot clinical trial to determine the necessary effect size for an appropriately powered definitive clinical trial that will be pursued in a subsequent R01 (or UG3/UH3) application submitted to the NIH. We plan to enroll a convenience sample of N=22/group. We note that prior definitive studies in this pain model have detected NSAIDs such as ibuprofen with a similar sample size (17, 18).

12.3. Populations for Analyses

Clearly identify and describe the analysis datasets (e.g., which participants will be included in each).

All participants in all three groups will be included in the analyses. The 3 groups will be compared to each other. While we expect that randomization will lead to balanced groups, we will specifically assess for age and sex balance and perform sensitivity analyses, if indicated. Further, we will employ generalized estimating equation models accounting for correlation between pain measures at various timepoints to assess the timepoint when maximum analgesia is observed.

12.4. Statistical Analyses

Include analysis of primary efficacy endpoints, secondary endpoints, safety analyses, and any planned interim analyses

This analysis will provide critical information for subsequent sample size calculations and endpoint determination in the subsequent main study. Mixed model analyses will be used for both primary and secondary outcomes. AEs among the groups will be analyzed with χ^2 tests. The time-to-rescue medication will be summarized using Kaplan-Meier curves and compared between groups using stratified log-rank tests. Level of significance will be set at $\alpha=0.05$. JMP software and GraphPad will be used for the analyses and the graphs.

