Adults 18-75 years old with moderate-severe odontogenic pain	
 -Healthy adults 18-75 years old, ASA I or II. -Permanent tooth with moderate to severe odontogenic pain, i.e. ≥30 on a 100mm VAS, as reported verbally by the patient. -Clinical pulpal diagnosis of irreversible pulpitis or pulpal necrosis, and periapical diagnosis of symptomatic apical periodontitis. -Test negative for recent cannabis use and/or other drugs of abuse including alcohol (urine tests collected at screening visit. Results will be available on site within 3-5 minutes). -Participant able to understand the forms (English or Spanish) and provide informed written consent 	
 -ASA Class III or IV, patients with hepatic impairment, pregnant or lactating women (pregnancy test is performed at the screening visit). -Patients on drugs metabolized by enzymes that also metabolize CBD (e.g. clobazam, diazepam, topiramate, warfarin), or other drugs known to interact with Epidiolex (as assessed by PI at time of screening). -Self-reported prior experience inhaling cannabis (either via smoking or vaporization). -Use of opioids in the month prior to screening/treatment visit, and/or NSAIDS or acetaminophen 6 hours prior to treatment. -Unwilling to participate
6.4. Will screen failures be allowed to re-screen at a later date?	 No  Yes If yes, describe criteria below ↓	Since the patients present with emergency pain and their pain will need to be addressed in a timely manner with appropriate treatment, there won't be any re-screening.

7. Study Intervention(s) being tested or evaluated

This can include prevention, diagnostic or therapeutic interventions (e.g., drug or device) or educational, health services or basic science interventions (e.g., educational program, health care delivery model, or examining basic physiology)

This is a therapeutic intervention study where the FDA approved study drug used off-label in two different doses according to randomization will be assessed against a Placebo of similar taste and appearance.

Group 1: CBD 10mg/kg single dose (given one time only) Epidiolex 100mg/ml oral solution

Group 2: CBD 20mg/kg single dose (given one time only) Epidiolex 100mg/ml oral solution

Group 3: Placebo oral solution single dose (given one time only)

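### Time-0 VAS should be prespecified as a baseline term in the VAS models: the primary outcome is a change from baseline, but neither planned model names one

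*Combined protocol and SAP*

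**What the plan says.** Section 3.1 lists as a primary outcome "VAS pain intensity differences from baseline among the groups at each time point", together with maximum pain relief. Section 3.2 has patients rate pain "using a 100mm Visual Analogue Scale (VAS) at 0, 15min, 30min" and at further readings up to 3 hours and 1 week: one pre-dose reading and eight post-dose readings.

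On analysis, section 12.4 says "Mixed model analyses will be used for both primary and secondary outcomes". Section 12.3 adds "generalized estimating equation models accounting for correlation between pain measures at various timepoints", with the stated aim of locating the time of maximum analgesia. Neither section says whether the modelled response is the raw VAS or the change, or whether time 0 is a response or a covariate. The only baseline variables named are age and sex, which are to be checked for balance, with sensitivity analyses if needed.

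Section 12.2 gives the purpose: "This is a pilot clinical trial to determine the necessary effect size for an appropriately powered definitive clinical trial". It sets 22 patients per group as a convenience sample, without a power, effect size or SD.

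**The concern.** The outcome is defined relative to baseline pain, yet baseline pain is the one prognostic measurement that the analysis sections do not mention. A natural reading is that changes from time 0 are computed and compared between arms with no further use of the baseline value. That fixes the baseline slope at 1, whatever slope the data support. When the true slope is below 1, which is usual when correlation is moderate, the change score carries baseline noise that a covariate would remove.

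What is at stake is precision and prespecification. The effect estimate and residual variance from 66 patients are meant to feed the sample size of a definitive trial. The wording also allows a raw-score, a change-score, a baseline-adjusted or a constrained-baseline model, so the choice could be made after the data are seen.

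**Working it through.** **Plan's own figure.** There is nothing to reproduce: 22 per group is a convenience sample with no stated inputs.

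**Inputs from the documents.** Three arms of 22 (section 12.2), 66 patients in all; equal allocation (section 7); VAS at time 0 and at eight later readings (section 3.2).

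**Assumed inputs.** rho is the correlation between baseline and a given follow-up reading. k is baseline SD divided by follow-up SD. The documents give neither. I take rho = 0.3, 0.5, 0.7 and k = 1, 0.8, 0.6. Values of k below 1 are plausible because entry requires "Permanent tooth with moderate to severe odontogenic pain, i.e. ≥30 on a 100mm VAS", which cuts off the lower part of the baseline distribution. Readings are taken as complete and unaffected by rescue.

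**Formulas, with follow-up SD set to 1.**

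- Change-score variance: 1 + k² − 2·rho·k.
- Baseline-adjusted variance before the slope cost: 1 − rho².
- Their difference: (1 + k² − 2·rho·k) − (1 − rho²) = (k − rho)². This is never negative, and it is zero only when k = rho.
- Cost of estimating one slope with three arms: 1 + 1/(66 − 3 − 2) = 1 + 1/61 = 1.0164, or about 1.6%.
- Net ratio: 1.0164·(1 − rho²) / (1 + k² − 2·rho·k).

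**Two cases worked through.** At k = 1, rho = 0.3: 1.0164 × 0.91 = 0.925; 1 + 1 − 0.6 = 1.40; 0.925/1.40 = 0.661. At k = 0.6, rho = 0.5: 1.0164 × 0.75 = 0.762; 1 + 0.36 − 0.60 = 0.76; 0.762/0.76 = 1.003.

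**Net variance ratio, adjusted to change score. In brackets, the number per arm that a change-score analysis would need to match 22 adjusted (22 / ratio).**

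| k | rho = 0.3 | rho = 0.5 | rho = 0.7 |
|---|---|---|---|
| 1 | 0.661 (33.3) | 0.762 (28.9) | 0.864 (25.5) |
| 0.8 | 0.797 (27.6) | 0.907 (24.2) | 0.997 (22.1) |
| 0.6 | 0.925 (23.8) | 1.003 (21.9) | 0.997 (22.1) |

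**Outside that grid.** At k = 1.25, rho = 0.3: 1 + 1.5625 − 0.75 = 1.8125; 0.925/1.8125 = 0.51.

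**Simulation check.** Three arms of 22, 20,000 runs per setting, gave 0.66, 0.76, 0.86 (k = 1); 0.80, 0.92, 0.99 (k = 0.8); and 0.93, 0.99, 1.00 (k = 0.6). With no true effect, both estimators averaged zero to within 0.005 follow-up SD.

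**Repeated readings.** With complete data on eight post-dose readings, generalized least squares with arm-by-time and baseline-by-time terms gave the same arm contrast at each reading as the single-reading adjusted analysis. The table therefore applies reading by reading, with that reading's own rho and k.

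**The case against.** The strongest reply is that baseline is not ignored. Defining the outcome as a change already removes it, with a slope of 1, and the resulting contrast is valid. The text does not rule out a covariate, and a mixed model with time 0 among the responses and a common mean there would fit the wording. This stands: the plan is under-specified rather than wrong, and the unadjusted change score is only one reading of a silent text.

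A second reply is that the size of the gain rests on assumed values. This also stands. Three of the nine settings show no practical gain, and one of those is a loss of 0.3%. A reader might take the roughly 34% reduction at k = 1, rho = 0.3 as a ceiling, or as the expected gain. It is neither, only the edge of a chosen grid. If k exceeds 1 the gain is larger, and that is possible at 1 week, after the planned dental treatment. Section 10.3 acknowledges that rescue analgesics lower pain, and patients who take them remain in the study (section 11.1). Rescue can therefore change the later rho and k in ways that these figures do not capture.

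A third reply is that section 12.4 leaves other items open too, such as the covariance structure. That is true, but it is no reason to leave this one open. The adjusted model uses data already in hand and risks at most about 1.6% in variance.

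**Conclusion.** The point holds as a precision and prespecification gap in the VAS analysis. Apart from about 1.6% in variance, an unadjusted change-score contrast is never more precise than the baseline-adjusted one. In the settings tabulated, the adjusted analysis ranges from no practical gain to about one third less variance, and to about half (ratio 0.51) at k = 1.25, rho = 0.3. All of these sizes are illustrative: they depend on assumed rho and k, and on complete readings unaffected by rescue. They do not cover maximum pain relief or the secondary scales.

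A reader might infer that the planned analysis is biased, or that the trial is underpowered because of it. The documents support neither. Randomization keeps the unadjusted contrast unbiased, and section 12.2 makes no power claim that could be undermined. No stated figure is wrong. The case for acting is that the pilot's product is an effect-size estimate, which this change may sharpen. The bite outcome is a separate matter and is not assessed here.

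**What to change.** In section 12.4, state one of two models for the VAS:

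1. A mixed model on the post-dose readings with arm, time, arm-by-time, baseline VAS and baseline-by-time, fitted regardless of observed balance. The baseline-by-time term lets the slope differ between 15 minutes and 1 week.
2. To the same end, a model of all readings including time 0, with arm means constrained equal at time 0.

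Time 0 must not be both a response and a covariate. If the GEE in section 12.3 is used to compare arms, give it the same baseline terms; locating the time of maximum analgesia does not by itself need them. The age and sex check can stay as a supplementary analysis.

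The cost is wording only, plus about 1.6% in variance for one slope with 66 patients. No further patients or measurements are needed.
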